To test gut permeability and absorptive capacity, lactulose-mannitol solution (containing 250 mg/mL lactulose and 50 mg/mL mannitol in purified water) will be administered to study participants orally at a

dose of 2ml/kg up to a maximum of 20 ml. Prior to administration of the solution, the child will be fasted for 30 minutes. Breast feeding will continue. A urine bag will be strapped to ensure all the urine is collected. The first urine sample voided will be considered as baseline. A new bag will then be put in place to continue urine collection for 2 hours. Once collected, an aliquot of 2 ml of urine will be stored between 2°C and 8°C having added 2 drops of chlorhexidine. Two hours after ingestion of LM solution, the test will be stopped. If the child has not passed any urine, the test time will be extended until the next urine is voided.

Following the LM test, two doses of PZQ will be administered three hours apart. After receiving praziquantel, all children will stay at the study premises for 3-6 hours with a guardian monitoring side effects. After administration of the second dose of the study product, children will undergo ultrasound scan to determine presence or absence of any pathology related to schistosomiasis. The Niamey Protocol will be used to grade severity of disease.

The subset of children (approximately N=150) who will be randomly selected for PK sampling (four blood draws in total) children will stay at the premises for at least 6 – 8 hours after administration of the initial dose of praziquantel. At the time of discharge, children who will be found to be infected with soil-transmitted helminths will be treated with albendazole 200 mg (12 – 24 month old children) or albendazole 400 mg (children over age two). Blood Chemistry to ascertain renal and liver function will be repeated 6 – 8 hours after administration of the first dose of praziquantel, before discharge.

2. *Study Visit 2.* Stool will be collected 4 weeks (+/- 1 week) after treatment. Two stools will be collected on consecutive days to quantify egg counts by Kato Katz. Field workers will be responsible for picking up cups at this timepoint. No visit to the field laboratories will be required. Urine will be collected for CCA/CAA. Blood (7 ml) will be collected for the same subset of N=150 subjects for studies of immunological responses as at baseline.

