- Final blood collection (3 ml) for CBC, renal, and liver toxicity 12 hours post dosing (all participants)

To participants further randomly selected for pharmacokinetics and immunology sub-studies:

- At each site participants will be randomly allocated into two groups with different blood sampling frequency but similar overall volume (an extra 5 ml)
 - Pharmacokinetic sub-study:
 - In a sub-set of children (N= 150 in both sites) the indwelling cannula will be used to obtain four blood samples of approximately 1 ml for PK/PD studies at respective intervals. Participants who will be sampled for PK/PD studies **will not** participate in the immunology sub-study
 - Immunology sub-study:

- In a sub-set of children in Uganda, 7 ml of whole blood will be collected for immunology assays (such as flow cytometry, Luminex, ELISpot and ELISA).
- Participants who will be sampled for the immunology sub-study **will not** participate in the PK/PD study
- A subset of children without schistosomiasis will be recruited and will provide urine before and after ingesting lactulose-mannitol solution. Stool and 4ml of blood will also be taken for study of gut microbiota/EED biomarkers and morbidity markers.

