7.5. Follow up at 6 months

The following activities will take place at the respective research laboratory. This visit will take approximately three hours with no overnight admission. Technical work in this phase will be performed by Ministry of Health personnel (Vector Control Division).

- **Admission** weight, height, clinical history
- **Stool** collection for:
 - Calprotectin and fecal occult blood (performed on site).
- **Urine** collection and storage for future processing of CAA. This will allow for monitoring of re-infection in the cohort.
- **PZQ or Placebo** administration at the study assigned dose after a meal consisting of local foods and monitoring for AE post-treatment

- **Blood:** Five ml for morbidity studies including CBC, iron biomarkers, EED biomarkers, pro-inflammatory cytokines and further 7 ml from the sub-group of N=150 children who were selected at baseline for immunology assays (such as flow cytometry, Luminex, ELISpot and ELISA). Before discharge, another blood sample will be removed between 6 – hours after administration of the first dose of the study drug. This enables monitoring for possible toxicity.
- **Ultrasound** to determine possible changes in baseline morbidity patterns

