9. ASSESSMENT OF SAFETY

9.1. Specification of Safety Parameters

Safety will be assessed by the frequency and severity of actively monitored and passively captured adverse events continuously in the 12 hours after every investigational product administration given throughout the duration of the trial. Parent reported adverse events during that time period will also be captured. This is made possible due to the continuous onsite presence of the trial doctor. The 12 hour duration is deemed sufficient monitoring since praziquantel is a moderately fast acting drug with elimination in less than 24 hours.

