9.4. Type and Duration of Follow-up of Subjects after Adverse Events

For subjects who are excluded based on chronic or acute medical condition or undernutrition, we will ensure follow up was secured at the community health center. The study field workers will re-visit the homes of these families to ensure follow up occurred.

For children found to have mild or moderate anemia, we will provide a 2-month supply of iron (mild) or 4 month supply (moderate) and we will recheck CBC at 6 month visit and repeat this approach based on laboratory findings.

We expect that adverse events related to drug dosing will resolve prior to discharge at 12 hours (enrollment) or 3-4 hours after dose (6 month visits).

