9.5. Halting Rules

Safety findings that would lead to temporary suspension of enrolment include:

- 1) A greater than expected number of total serious adverse events deemed associated with the study product as defined by two or more SAEs associated with the study product among the first 20 children enrolled and then five or more serious adverse events among children, associated with the intervention per 100 children enrolled (5%).
- 2) 15 subjects per 100 enrolled experiencing adverse drug events as defined by a) an unexpected adverse event, as defined by a clinical adverse event (not a laboratory defined adverse event) that is not listed as expected with treatment, that occurs within 2 days after dosing, If the total number of unexpected adverse drug events occurs among 15 children per 100 enrolled or 15% or more of children, halting rules would apply.

If either of the above occurs, this would lead to temporary suspension of enrolment and a safety review (either routine or ad hoc), the objective of which is a decision as to whether the study (or intervention for an individual or study cohort) should continue per protocol, proceed with caution, be further investigated, be discontinued, or be modified and then proceed. Suspension of enrollment (for a particular group or for the entire study) is another potential outcome of a safety review.

Subsequent review of serious, unexpected, and related AEs by the Medical Monitor, DSMB, IEC/IRB, the sponsor(s), or relevant local regulatory authorities may also result in suspension of further trial interventions/administration of study product at a site. The study sponsor(s) retain the authority to suspend additional enrollment and study interventions/administration of study product for the entire study, as applicable.

Individual Halting Rules

A child will be discontinued from the study if he/she experiences a severe allergic/anaphylactic reaction to any dose of Praziquantel given during the study (enrolment or six months).

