9.6. Safety Oversight (ISM plus SMC or DSMB)

Independent safety oversight will be under the direction of a DSMB composed of individuals with expertise in clinical pediatrics, schistosomiasis, biostatistics, and clinical trials methodology. The DSMB will be engaged until the last patient is enrolled and treated at baseline. We expect this will be about 18-24 months. An independent safety monitor (ISM) will be identified in Uganda and The Philippines. The individuals will be physicians, independent of the trial, and live in close proximity to the study activities. The DSMB will operate under the rules of an IRB-approved charter that will be written at the organizational meeting of the DSMB. The DSMB will set the frequency of planned meetings and establish safety criteria for additional ad hoc meetings. The DSMB will advise PIs and IRBs of its findings. The DSMB had a first meeting to review the protocol and develop the charter on June 14, 2019. DSMB suggestions for changes to the protocol are reflected in this protocol.

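### Halting rule 2 counts events to 2 days while planned capture stops at 12 hours, and the three-hour six-month visit cannot hold its own listed procedures

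*Combined protocol and SAP*

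**What the plan says.** **Halting rule and capture**
- Section 9.5, rule 2, suspends enrolment when 15 children per 100 have an unexpected clinical event "that is not listed as expected with treatment, that occurs within 2 days after dosing".
- Section 9.1 sets active and passive capture "continuously in the 12 hours after every investigational product administration given throughout the duration of the trial", limits parent reports to the same period and calls it sufficient. The outcome measure in 3.2.2 also uses 12 hours.
- Section 7.4 (week 4) lists stool, urine and, for a subset, blood. It lists no adverse-event questions.

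**Six-month visit**
- Section 7.5: "This visit will take approximately three hours with no overnight admission". The same section plans a toxicity blood sample from 6 hours after the first dose.
- Table 1 and the arm descriptions in 4.2.1 give every arm two administrations 3 hours apart at this visit.

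**Related statements**
- Baseline stay: 12 hours in 2.3.1, 7.3 and 9.4, but in 4.2.1 "all children will stay at the study premises for 3-6 hours with a guardian monitoring side effects".
- Discharge in 9.4, where drug-related events are expected to "resolve prior to discharge at 12 hours (enrollment) or 3-4 hours after dose (6 month visits").
- Post-dose toxicity blood: in 4.2.1, "Blood Chemistry to ascertain renal and liver function will be repeated 6 – 8 hours after administration of the first dose"; in 7.3, "Final blood collection (3 ml) for CBC, renal, and liver toxicity 12 hours post dosing (all participants"). Sections 3.1.2 and 3.2.2 specify 12 hours.
- Adverse-event hypotheses in 11.1: events within 3 hours of dosing, without saying which of the two doses.
- DSMB term: section 9.6 says "The DSMB will be engaged until the last patient is enrolled and treated at baseline", while 9.6.2 gives the board a final review after database lock.

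**The concern.** A halting threshold works only if the events it counts are looked for over the whole period it counts them. Here the rule looks out to 2 days and the planned capture does not. The numerator would then be too small and the 15% trigger less likely to be met at any given true rate. The population is one that section 2.3.1 calls vulnerable, and the same section names the higher dose as the primary risk.

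The six-month visit raises a different problem. Sites cannot follow both the stated visit length and the stated procedures, so something will be dropped or improvised, possibly differently in Uganda and the Philippines. The remaining inconsistencies leave the safety endpoints without one agreed observation time.

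**Working it through.** **1. The plan's own threshold.** 15/100 = 15%, as section 9.5 states.

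**2. Halting window against planned capture.** Rule window: 2 days = 48 h (9.5). Planned capture: 12 h (9.1, 3.2.2). With both counted from the same dose, 48 − 12 = 36 h have no planned capture, and 36/48 = 75% of clock hours. If the rule runs from the first dose and capture runs to 12 h after the second (3 + 12 = 15 h), the gap is 48 − 15 = 33 h.

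**3. Direction of the effect on the rule (illustration only).** Let p be the true 48-hour rate of children with an unexpected clinical event and f the share of those children whose event is captured. The documents give neither, so both are assumed. Treating the rule as one look at 100 children, the chance of reaching the threshold is P(X ≥ 15) with X ~ Binomial(100, p·f).

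| p | f = 1 | f = 0.90 | f = 0.75 | f = 0.50 |
|---|---|---|---|---|
| 0.15 | 54% | 37% | 15% | 0.8% |
| 0.20 | 92% | 82% | 54% | 7% |
| 0.25 | 99% | 98% | 86% | 26% |

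Missing events can only lower the chance of a halt. How far depends on f, which is unknown.

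**4. Shortest possible six-month visit.** Put the first dose at 0 h.
- Second administration: 3 h. This alone uses the stated visit length.
- Toxicity blood: 6 h at the earliest, and 6/3 = 2 times the stated length. With the meal that 4.2.1 places about half an hour before dosing, 6 + 0.5 = 6.5 h.
- Twelve hours of monitoring after every administration (9.1): 3 + 12 = 15 h after the first dose.
- Discharge 3–4 h after dose (9.4): 3–4 h if counted from the first dose, which is before the blood sample; 6–7 h if counted from the second, which exceeds the stated visit.

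**5. Baseline stay.** The 3–6 h in 4.2.1 ends 3–6 h after the first dose, or 6–9 h after it if the stay runs from the second dose. Neither reaches the 12 h in 2.3.1, 7.3 and 9.4.

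**6. Adverse-event analysis window.** Three hours from the first dose ends when the second administration is due, and at baseline that administration is the only difference between the 40 and 80 mg/kg groups. Three hours from the second dose ends 3 + 3 = 6 h after the first, outside a three-hour visit. Either way it differs from the 12 h in 3.2.2.

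**7. DSMB term.** Assume uniform enrolment over T months and no attrition. Six-month visits falling after the last baseline treatment = 600 × 6/T.
- T = 24: 600 × 6/24 = 150.
- T = 18 (9.6 expects 18–24): 600 × 6/18 = 200.
- Half are active re-doses (arms 2 and 4, 300 of 600): 75 and 100.

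Applying in full the 10% attrition that 11.2 uses for the later endpoints gives 135–180 visits, about 68–90 of them active.

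**The case against.** Several stronger readings are tempting, and the documents do not support them.

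- *Late events cannot trigger the rule because nobody collects them.* Too strong. The unscheduled-visit text in section 7.10 lets families make contact at any time and mentions safety concerns, 9.2.1 allows events to come to notice at study visits, and serious-event reporting (9.3.1) has no 12-hour limit. Rule 1, which counts serious events, is not affected. What stands is that no scheduled contact found in the text asks about hours 12 to 48.
- *Three quarters of events are lost.* The 75% is a share of clock hours. Section 9.1 defends 12 hours by drug elimination in under 24 hours, so events may cluster early.
- *Repeat-dose safety cannot be interpreted.* No stated hypothesis compares baseline with six-month event rates. The formal tests compare dose groups, which share the same observation schedule at each visit, so a distorted randomised contrast has not been shown.
- *The toxicity-blood times flatly contradict each other.* Section 7.3 lists a draw from 6 hours and a final draw at 12 hours, and may intend both. The conflict with the stay and draw in 4.2.1 remains.
- *Oversight ends with the last baseline dose.* The independent safety monitor serves for the whole study (9.6.1), the Medical Monitor reviews serious events in real time (9.6.2), and sponsors and ethics boards can suspend dosing (9.5). The two statements of the DSMB term still disagree.

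Also fair: Appendix A shows only its heading in the copy reviewed, and the manual of procedures is not included. Either might schedule a later contact. That would not remove the 12-hour limit in 9.1 or the three-hour visit in 7.5.

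**Conclusion.** The point holds as a set of conflicts between operative sections, two of them firm.

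First, halting rule 2 counts to 48 hours while planned capture covers 12. The count is incomplete over the other 36 hours and biased towards not halting. The size of that bias cannot be estimated, because the documents give no event-time distribution; the binomial figures rest on assumed rates and capture shares and show direction only.

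Second, the six-month visit needs at least 6 hours for its own procedures against about 3 stated. This rests on no assumption beyond the protocol's times; the missing upper limit on the blood-draw interval does not matter, since the lower limit alone exceeds the visit.

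The baseline stay, toxicity-blood time, adverse-event analysis window and DSMB term are secondary conflicts. The 150–200 visits (75–100 active) after the DSMB end point in 9.6 depend on uniform enrolment over 18–24 months and no attrition.

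**What to change.** The sponsor should reconcile sections 2.3.1, 3.1.2, 3.2.2, 4.2.1, 7.3, 7.5, 9.1, 9.4, 9.5, 9.6, 9.6.2 and 11.1 so that:

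- the halting-rule window and the event-capture window agree;
- the stated six-month visit length agrees with the procedures listed for it;
- the baseline stay is the same wherever it is given;
- the toxicity-blood times agree with the endpoint, and the text says whether one draw or two is meant;
- the adverse-event analysis window names the dose it runs from and agrees with the outcome measure;
- the two statements of the DSMB term agree.

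Which window, time or term is adopted is for the sponsor to decide. The cost is an amendment to wording, and possibly a longer six-month visit if the listed procedures are kept.

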Three events were denoted “severe” (vomiting (2) and vertigo) in the 75 mg/kg dose group which had N = 45 children; no Serious Adverse Events as defined by death, life threatening event, need for hospitalization, or persistent morbidity/incapacity, were reported in either group. The reported rates of adverse events were slightly higher in the 75 mg/kg group than the 40 mg/kg comparison group. In a separate recently published study in Cote D’Ivoire, escalating doses of praziquantel (20, 40, 60 mg/kg) were examined in a cohort of children including pre-school age children (PSAC) aged 2-6 years.¹² Among PSAC, adverse events were mild with fewer adverse events observed three hours post-treatment compared to pre-treatment. Importantly, the number of adverse events was similar among the three praziquantel treatment doses, with fewer adverse events observed in the placebo-treated groups. Only mild expected adverse events were reported with the exception of one moderate grade adverse event 3 hours after the first praziquantel dose in one PSAC (diarrhea). No serious adverse events were noted at any dose. We will minimize risk by “admitting” children for observation with active and passive assessment for adverse events for 12 hours. We will also provide children with a meal to minimize side effects. **Finally, we will administer the 80 mg/kg dose as two doses of 40 mg/kg split over three hours.**

There is also a small risk to young children from blood draw, which is due to iron deficiency anemia as a blood draw removes red blood cells and iron. This risk is minimal given the small amount (7 – 12 ml) that will be drawn at each of three time points, representing 20 – 25 ml in a year. For the immunology study subpopulation, an extra blood draw of 7ml will be made at 4-week follow up time point. Very minimal risks are associated with venipuncture itself, which will be performed by trained medical personnel.

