3. *Study Visit 3 (6 months post enrolment)* Six months (+/- 2 weeks) following visit one, subjects will return to the respective field laboratories. They will receive either the same dose of Praziquantel as received at Visit 1 or placebo as determined at baseline randomization. At this

visit, and before the study drug or placebo is received, blood will be drawn for follow up assessment of morbidity, and in depth measures of nutritional status. An ultrasound scan will be performed. Blood (7 ml) will be collected for the same subset of N=150 subjects for studies of immunological responses. Urine will be stored at this visit for future processing of CAA to monitor re-infection.

4. Study Visit 4, Close out. (12 months post enrollment) Twelve months (+/- 2 weeks) post enrollment and initial treatment, study subjects will return to the field laboratory. Prior to this visit they will be asked to provide three stool samples and one urine. At this visit, blood will be drawn for follow up morbidity studies and in-depth measures of nutritional status will be made. All children will be treated with Praziquantel and those infected with soil-transmitted helminths will be treated with albendazole 200 mg (12 – 24 month old children) or albendazole 400 mg (children over age two). A repeat ultrasound scan will be done before the participant is discharged from the study. If however, the ultrasound scan at six months revealed resolution of any pathology detected at baseline, there will be no repeat at discharge. Blood (7 ml) will be collected for the same subset of N=150 subjects for studies of immunological responses.

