5.3.3. Reasons for Withdrawal and Discontinuation of Study Product Administration

Subjects may voluntarily withdraw their consent for study participation at any time without penalty or loss of benefits to which they are otherwise entitled.

An investigator may also withdraw a subject from receiving the study product for any reason. Follow-up safety evaluations will be conducted, if the subject agrees. If a subject withdraws or is withdrawn prior to completion of the study, the reason for this decision must be recorded in the case report forms (CRFs).

The reasons, might include, but are not limited to the following:

- Subject no longer meets eligibility criteria
- Subject becomes noncompliant
- Medical disease or condition, or new clinical finding(s) for which continued participation, in the opinion of the investigator might compromise the safety of the subject, interfere with

the subject's successful completion of this study, or interfere with the evaluation of responses

- Subject lost to follow-up
- Determined by a physician's discretion to require additional therapy not indicated in the protocol to ensure subject's health and well-being (or treatment failure, if applicable)
- Voluntary withdrawal

If the subject consents, every attempt will be made to follow all AEs through resolution. The procedures that collect safety data for the purposes of research are included in the informed consent.

Investigators will inform the subject that already collected data will be retained and analyzed even if the subject withdraws from this study, unless they withdraw consent.

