5.3.4. Handling of Withdrawals and Discontinuation of Administration

If subjects are withdrawn by study investigators due to newly diagnosed medical condition, they will be referred for treatment at the respective district hospitals. Subjects who voluntarily withdraw consent will be offered follow up screening for schistosomiasis and soil transmitted helminths and treatment provided as needed. No other nutritional or morbidity studies will be conducted as these are research only. In the unlikely event that a subject needs to discontinue product administration at later time points due to an AE or SAE, he/she will be asked to continue scheduled evaluations, complete an end-of-study evaluation, and be given appropriate care for symptoms of any AE until resolved or the subject's condition becomes stable.

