5.3.5. Subject Replacement

Subjects withdrawn will not be replaced. Our sample size calculations allowed for withdrawal and expected rates of loss to follow up.

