This sample size will give 80% power to detect differences in the secondary morbidity outcomes measures. We increase the estimated loss to follow up for these endpoints given they occur at six and 12 months following treatment. With 10% attrition, we will have 540 subjects at the 12 month follow up. As one example of the effect size we will detect for the key secondary outcome of weight-for-height z-score at 12 months, we will have 80% power to detect a difference in mean weight-for-height z-score between the six-monthly and 12-monthly dosing groups as low as 0.24 z-score, assuming a standard deviation of 1 and two-sided significance level 5% between children who received six-monthly praziquantel (either 40 mg/kg or 80 mg/kg) and children who received 12-monthly praziquantel (either 40 mg/kg or 80 mg/kg). A weight for age z-score difference of 0.23 is biologically relevant, particularly based on mitigation of only one cause of nutritional morbidity in this setting. For hemoglobin, we will be able to detect a difference of 0.29 g/dL using a standard deviation of 1.2, power of 80%, and functional sample size of 540.

For the PK study, 137 children from both sites (Uganda/Philippines) will be sampled. These are the numbers needed for 80% power to show a slope of the relationship between log CAA at 24 days and AUC is significant to $p < 0.05$. We will include 150 children to allow for loss to follow-up and enable sufficient power.

To assess immunological responses, assuming an SD of 0.9, the sub-study would require a sample size of 104 to achieve 80% power at 5% significance level for detecting difference in mean of $0.35\log_{10}$ cytokine response between the groups. We will recruit 150 children to allow for attrition.

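### Section 9.5 removes a child with a severe allergic reaction from the study; this contradicts Section 5.3.4 for baseline reactions and loses month-12 outcomes for six-month reactions

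*Combined protocol and SAP*

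**What the plan says.** In Section 9.5, the part that deals with a single child rather than the whole trial says: "A child will be discontinued from the study if he/she experiences a severe allergic/anaphylactic reaction to any dose of Praziquantel given during the study". The rule names both enrolment and six months.

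Section 5.3.4 covers a child who has to stop product at later time points because of an AE or SAE: "he/she will be asked to continue scheduled evaluations, complete an end-of-study evaluation". It makes no exception for allergy, and neither section refers to the other.

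Section 11.4 analyses all children as randomised, whatever treatment they received. It includes only those with outcome data and plans no imputation. The reason it gives is low expected loss at 4 weeks.

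Section 11.1 tests secondary hypotheses 6 to 13 on month-12 morbidity, for six-monthly versus 12-monthly treatment and for 40 versus 80 mg/kg.

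On attrition, Section 5.3.5 says: "Our sample size calculations allowed for withdrawal and expected rates of loss to follow up". Section 11.2 says: "With 10% attrition, we will have 540 subjects at the 12 month follow up".

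**The concern.** Stopping a drug and leaving a trial are different events, and the protocol treats them so. Section 5.3.3 speaks of withdrawing a child from receiving product. Section 5.3.4 ends the nutritional and morbidity work only for families who withdraw consent. Section 9.5 crosses that line for one kind of event. A site that followed it literally would stop collecting outcomes on a child because of a reaction to the treatment.

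An intention-to-treat comparison depends on outcomes being collected after product stops. With complete cases and no imputation, a child sent home under Section 9.5 drops out of the analysis, and the reason is treatment-related. At stake are agreement between site conduct and the declared analysis, and unambiguous instructions for an event that staff must handle quickly.

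**Working it through.** **Step 1. Baseline reaction.** A child who reacts severely at enrolment cannot be given the six-month dose.

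- The trigger in 5.3.4 is met: product is stopped at a later time point because of an AE or SAE. The child stays in scheduled evaluations.
- The trigger in 9.5 is also met. The child leaves the study.
- The two instructions are opposite. Under 9.5 the week-4 stool for the primary endpoint and the month-6 and month-12 visits are all lost.

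**Step 2. Six-month reaction.** The Study Visit 3 text in Section 4.2.1 says: "before the study drug or placebo is received, blood will be drawn for follow up assessment of morbidity". Month-6 morbidity data are therefore already in hand, and only month 12 is exposed. No randomised visit dose follows month 6, so it is unclear whether 5.3.4 applies. Here 9.5 acts alone.

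**Step 3. Which arms.** At six months Arms 1 and 3 receive placebo at both doses, while Arms 2 and 4 receive praziquantel (Table 1). The rule requires a reaction to praziquantel, so removal at this visit can occur only in Arms 2 and 4. Those arms together form the six-monthly group.

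**Step 4. Scale: power.** Inputs from Section 11.2: 600 × 0.90 = 540 children at 12 months, SD 1, two-sided 5%, 80% power. With two equal groups, SE = √(4/N).

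- Plan's own figure: (1.960 + 0.842) × √(4/540) = 0.241, which agrees with the stated 0.24.
- Power at a difference of 0.24 is Φ(0.24/SE − 1.960).

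| Children lost beyond plan (assumed) | N | Detectable difference | Power at 0.24 |
|---|---|---|---|
| 0 | 540 | 0.241 | 79.6% |
| 6 | 534 | 0.2425 | 79.2% |
| 12 | 528 | 0.244 | 78.7% |

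If the removals fall within the planned 10%, power does not change.

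**Step 5. Scale: bias in six- versus 12-monthly.** Arms 2 and 4 hold 300 children, or 270 after 10% attrition. Suppose k of those 270 are missing and average 1 SD below the rest of their group. The observed group mean is then too high by k/270:

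- k = 1: 0.004 z
- k = 3: 0.011 z
- k = 6: 0.022 z

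The planned detectable difference is 0.24 z. Both k and the 1 SD offset are assumptions; the documents give no rate of severe allergic reaction.

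**The case against.** **A specific rule may override a general one.** Section 9.5 could be a deliberate exception for one extreme event, or loose wording for stopping product. Either is possible. But 5.3.4 has no carve-out and there is no cross-reference, so a site cannot tell which is meant.

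**The contradiction is narrower than it looks.** This stands. It is clear only for baseline reactions. For a six-month reaction the problem is loss of month-12 data under 9.5, not two rules in conflict.

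**The complete-case rule is argued only for 4 weeks, and a formal SAP was still to come.** This also stands. Applying it to month 12 is an interpretation, although Section 11.4 gives no other method for that time point.

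**Safety care is not abandoned.** Section 9.3.1 follows SAEs to resolution. The point concerns outcome data.

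A reader might infer two stronger claims, and the documents support neither.

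- *Other investigator stops also end follow-up.* For a new diagnosis, Section 5.3.4 says: "If subjects are withdrawn by study investigators due to newly diagnosed medical condition, they will be referred for treatment at the respective district hospitals". For product stops generally, Section 5.3.3 says: "Follow-up safety evaluations will be conducted, if the subject agrees". Neither mentions outcome visits, but neither rules them out. Section 5.3.3 withdraws the child only from product, and 11.4 keeps children whatever they received. This is missing detail.
- *The loss biases 40 versus 80 mg/kg.* Both dose groups receive the same first 40 mg/kg, so only a reaction to the second dose could differ between them. No document links allergy to dose; the severe events at 75 mg/kg in the study cited in Section 2.3.1 were vomiting and vertigo. Even in an extreme case the effect is limited. Take 279 children in a dose group at week 4 (300 less 7%), a true cure rate of 82%, and k uncured children all missing from that group. The observed rate is 0.82 × 279/(279 − k), which is 82.3%, 82.9% or 83.8% for k = 1, 3 or 6. The largest shift is 1.8 points, against a planned difference of 12.

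**Conclusion.** The point holds and is minor. For a severe allergic reaction at baseline, 9.5 and 5.3.4 give opposite instructions. For one at six months, 9.5 would cost the month-12 outcomes, in Arms 2 and 4 only. Followed literally, the rule removes treatment-related cases from an analysis described as intention-to-treat.

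The number of children cannot be derived from the documents and is probably very small. Of the cited comparison of 75 with 40 mg/kg, Section 2.3.1 reports: "no Serious Adverse Events as defined by death, life threatening event, need for hospitalization, or persistent morbidity/incapacity, were reported in either group". That is limited evidence, since there were 45 children at 75 mg/kg and they were aged 10 to 15 years. On the assumed counts the effect on power is negligible, and the shift in the six- versus 12-monthly comparison is at most 0.022 z for six children. The case for change rests on consistency and retention of data, not on a material threat to the results.

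**What to change.** In Section 9.5, replace removal from the study with permanent discontinuation of praziquantel, including the month-6 and month-12 doses. State that scheduled evaluations continue as in 5.3.4 unless consent is withdrawn or a particular procedure is unsafe for that child. Analyse the child in the randomised arm.

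The month-12 exemption must be explicit. The Study Visit 4 text in Section 4.2.1 and Section 7.7 have all children treated at 12 months, and Section 7.6 has infected children treated. A child kept in follow-up after anaphylaxis could otherwise be dosed again.

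The cost is a wording change, using visits that are already scheduled, and modest effort to bring back children who are off product. It will not recover families who stop attending.
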